#### Juniper Asthma Control Questionnaire (ACQ)

The 5-question version of the Juniper ACQ (ACQ-5) is a validated questionnaire to evaluate asthma control. The ACQ-5 has 5 questions which assess the top-scoring five asthma symptoms:

- Frequency in past week awoken by asthma during the night
- Severity of asthma symptoms in the morning
- Limitation of daily activities due to asthma
- Shortness of breath due to asthma
- Frequency of wheezing

Patients are asked to recall how their asthma has been during the previous week and to respond to the symptom questions on a 7-point scale (0=no impairment, 6= maximum impairment).

A global score is calculated: the questions are equally weighted and the ACQ-5 score is the mean of the 5 questions and, therefore, between 0 (totally controlled) and 6 (severely uncontrolled). A higher score indicates lower asthma control. Scores less than 1.0 reflect adequately controlled asthma, and scores 1.0 or greater reflect inadequately controlled asthma. On the 7-point scale of the ACQ-5, a change or difference in a score of 0.5 is the smallest change that can be considered clinically important, corresponding to the Minimal Clinically Important Difference (MCID) defined by the developer. The recommended change of 0.50 is a reasonable threshold to define a meaningful individual-level change.

Based on the manual of ACQ, any more than one missing value is not acceptable. If more than one of the questions has a missing value, the global score is invalid and will be considered as missing. If only one question has a missing value, it will be interpolated (pro-rated) using the completed questionnaires from the previous visit. For example, if answer to question 5 is missing at week 24 visit and all questions are completed at week 12 visit, the score for question 5 at week 24 visit will be imputed as: (sum of score at week 24 visit/sum of scores excluding question 5 at week 12 visit) × score of question 5 at week 12 visit. If the questionnaire from the previous visit is not complete, the missing value will be imputed as the average of the completed questions within the current visit.

The ACQ-5 will be administered only to patients with a documented history of asthma. It will be completed by patients using electronic questionnaires at the baseline visit (visit 3), week 12, week

24, week 36, and week 52 (EOS) or ET visits, and immediately prior to start of rescue medication or procedures.

Standardized Rhinoconjunctivitis Quality of Life Questionnaire for ages 12+ [RQLQ(S)+12]

RQLQ(S)+12 is a self-administered questionnaire to measure health-related QOL in those 12 years of age and above, as a result of perennial or seasonal allergic rhinitis. There are 28 items on the RQLQ(S) in 7 domains: activity limitation, sleep problems, nasal symptoms, eye symptoms, non-nasal/eye symptoms, practical problems, and emotional function. The RQLQ(S)+12 responses are based on a 7-point Likert scale with responses ranging from 0 (not troubled) to 6 (extremely troubled). The overall RQLQ(S)+12 score is the mean of all 28 responses and the individual domain scores are the means of the items in those domains. No interpolation will be performed for missing scores. Higher scores indicated more health-related QOL impairment (lower scores were better). A change of 0.5 point or more in total score is considered to be clinically meaningful.

The RQLQ(S)+12 will be administered only to patients with a documented history of allergic rhinitis. It will be completed by patients using electronic questionnaires at the baseline visit (visit 3), week 12, week 24, week 36, and week 52 (EOS) or ET visits, and immediately prior to start of rescue medication or procedures.

Pain related to dysphagia

Pain related to dysphagia is assessed daily by question 4 in the DSQ questionnaire. Patient will respond to this question only when they answer Yes to question 2 “Since you woke up this morning, has food gone down slowly or been stuck in your throat?”. If the answer is No to question 2, a score of 0 will be assigned to pain related to dysphagia. The pain score over a 14-day period is calculated using the formula:

$$\text{Dysphagia Related Pain Score} = \frac{(\text{sum of points from question 4 from daily DSQ diary}) \times 14 \text{ days}}{\text{number of diary days reported with non-missing data}}$$

The rules for a minimum of 8 diary entries and non-missing data are the same as used for DSQ score calculation as described in Section 4.4.1.

Endolumenal Functional Lumen Imaging Probe (EndoFLIP)

The endolumenal functional lumen imaging probe (EndoFLIP, Medtronic, USA) device is a catheter-based procedure that measures the cross-sectional area at multiple sites along the esophagus with simultaneous intraluminal pressure recordings during volumetric distension of the esophagus. The analyses of cross sectional area versus pressure relationships of the esophagus allow for determination of esophageal compliance as well as the distensibility plateau. Distensibility Plateau (DP), Restricting Diameter 40mmHg (RD40) and Restricting Diameter 30mmHg (RD30) are collected to evaluate the distensibility of the esophageal body using EndoFLIP in the study. DP is the number at which the narrowest diameter measurement fails to expand anymore despite increasing intra-balloon pressure. RD40/RD30 is the narrowest diameter in the esophageal body at an intra-balloon pressure of 40mmHg/30mmHg (+/- 2mmHg). EndoFLIP may be performed for patients at selected North American, with measurements taken as part of the esophagogastrosocopy procedure performed at screening, week 24 and week 52. Procedural order should be: EREFS/imaging, EndoFLIP, then biopsies.

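### The SAP's rule for one missing ACQ-5 item has no value when the previous visit's other four items sum to 0, and can give an item above the scale maximum of 6

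*SAP*

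**What the plan says.** The SAP, section 4.4.3, under Juniper Asthma Control Questionnaire (ACQ), scores each of the five items from 0 to 6, takes the ACQ-5 score as their mean, and states that the score therefore also lies between 0 and 6. With more than one item missing, the score is set to missing.

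For a single missing item the rule is: "If only one question has a missing value, it will be interpolated (pro-rated) using the completed questionnaires from the previous visit". The worked example has question 5 missing at week 24. Its imputed value is the ratio "sum of score at week 24 visit/sum of scores excluding question 5 at week 12 visit" multiplied by the "score of question 5 at week 12 visit".

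There is one fallback: "If the questionnaire from the previous visit is not complete, the missing value will be imputed as the average of the completed questions", meaning those answered at the same visit.

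The protocol (section 8.2.2.9) describes the ACQ-5 score as the mean of five items and gives no missing-item rule.

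**The concern.** A pro-rating rule built on a ratio needs two safeguards: something to do when the denominator is 0, and a limit that keeps the result on the item's scale. The SAP text has neither.

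A zero denominator is a plausible clinical state. ACQ-5 goes to anyone with a documented history of asthma, current symptoms are not required, and the SAP labels a score of 0 as total control. A patient with no symptoms on four items at week 12 has a complete questionnaire, so the fallback is not triggered.

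Overflow occurs when a patient worsens from a low base. The imputed item then enters the five-item mean with no bound, although the same paragraph says that the score cannot exceed 6.

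In either case the programmer would have to devise a rule that the SAP exists to fix in advance. At stake is the accuracy of the ACQ-5 change from baseline, which section 4.4.3 lists as an exploratory endpoint at week 24 and again at week 52.

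**Working it through.** The SAP reports no figure to reproduce here, so the check applies its rule to possible answers.

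**Inputs, all from the ACQ text in SAP 4.4.3**
- Items are scored 0 to 6, and the score is the mean of 5 items.
- P = sum of the other four items at the previous visit (0 to 24).
- C = sum of the four answered items at the current visit (0 to 24). The week 24 sum has to be read this way, since question 5 is missing at that visit.
- q = previous value of the missing item (0 to 6).
- Smallest clinically important change in the score: 0.5.

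**Rule:** imputed item = (C / P) × q; score = (C + imputed item) / 5.

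**Undefined case.** With P = 0 the rule divides by zero for any C and q. A patient with 0 on every item at both visits gives (0 / 0) × 0, although four answered zeros now and five zeros before point plainly to 0. The fallback would give C / 4 = 0, but its condition (an incomplete previous questionnaire) is not met.

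**Overflow.** Each case below starts from valid answers.

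| P | C | q | Imputed item | Score as written | Score with item limited to 6 |
|---|---|---|---|---|---|
| 4 | 12 | 3 | 12/4 × 3 = 9 | (12 + 9)/5 = 4.2 | (12 + 6)/5 = 3.6 |
| 4 | 8 | 4 | 8/4 × 4 = 8 | (8 + 8)/5 = 3.2 | (8 + 6)/5 = 2.8 |
| 1 | 7 | 1 | 7/1 × 1 = 7 | (7 + 7)/5 = 2.8 | (7 + 6)/5 = 2.6 |

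In the first row the missing limit moves the score by 4.2 − 3.6 = 0.6, which is more than 0.5. The algebraic extreme is P = 1, C = 24, q = 6: an item of 24/1 × 6 = 144 and a score of (24 + 144)/5 = 33.6.

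**All combinations.** Enumerating all 7^4 × 7^4 × 7 = 40,353,607 answer patterns with equal weight, 16.0% give an item above 6, 1.9% give a score above 6, and 0.04% are undefined. Patients do not answer uniformly, so these shares only describe how the formula behaves. They do not forecast how often it fails.

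**What happens to an undefined score.** If the item is left missing, so is the score. SAP 5.6.5 sends exploratory variables to the methods of 5.6.1 and 5.6.2. Section 5.6.2 multiply imputes continuous data measured repeatedly up to week 24. ACQ-5 is collected at baseline, week 12 and week 24, so it falls under that rule. For Part C, section 5.6.2 summarises observed values and imputes nothing.

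**The case against.** **The ACQ manual may settle it.** The SAP bases its missing-item handling on that manual and introduces the formula as an example, so the edge cases might be covered there or in programming specifications. The manual is not available here, and this cannot be excluded. The SAP text itself, however, brings in no zero-denominator rule and no limit.

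**Single missing items may be rare.** ACQ-5 is normally completed electronically. This is a fair point about size. The SAP nevertheless writes a rule for the case, and protocol 8.2.2.9 also allows COVID-19 telephone interviews recorded on paper.

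**A reader might infer that these patients drop out of the week 24 analysis.** The documents do not support that. A missing score is multiply imputed and the patient stays in. What is lost is the information in four answered items. Only in the Part C summaries would the score be absent, and those are descriptive.

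**A reader might also infer that the failure is common, or that impossible values dominate the mean among asthma patients.** The documents give no ACQ item means, no single-item missing rate and no number of patients with an asthma history. The frequency depends on what is assumed. If the items are taken as independent binomial scores out of 6, the chance that four are all 0 is 0.95^24 = 29% at an item mean of 0.3 and 0.817^24 = 0.8% at a mean of 1.1. Correlation between items would raise both figures. No frequency can be claimed.

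**Materiality.** ACQ-5 change is exploratory and is not in the testing hierarchy of SAP 5.6.3. This stands in full: no confirmatory conclusion is touched.

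**Conclusion.** The point holds as a minor gap in the specification. As written, the rule is undefined for a complete previous questionnaire whose other four items sum to 0, and moderate worsening from a low base can push the imputed item above 6. No other section repairs either case. Both results follow from the formula alone; the one reading required is that the current-visit sum means the four answered items.

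For an affected patient the distortion can exceed the SAP's 0.5-point threshold (0.6 points in the first example above). Across the trial its size is unknown, because it is confined to patients with an asthma history and exactly one missing item.

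**What to change.** Add one sentence to the ACQ paragraph of SAP 4.4.3: if the previous visit's sum of the other four items is 0, impute the missing item as the mean of the completed items at the current visit (the existing fallback); otherwise truncate the pro-rated item at 6.

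The overflow part should be truncation and not the fallback mean, because switching to the mean above 6 would make the score improve as the patient worsens. Take a previous sum of 4 and a previous item of 3. A current sum of 8 gives an item of 8/4 × 3 = 6 and a score of (8 + 6)/5 = 2.8. A current sum of 9 gives 9/4 × 3 = 6.75. Replacing that with the mean, 9/4 = 2.25, gives a score of (9 + 2.25)/5 = 2.25, which is 0.55 lower for a patient who is one point worse. Truncation gives (9 + 6)/5 = 3.0 and keeps the order.

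The cost is that sentence and the matching line of code. No new data are needed.

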### Prorated/un-prorated DSQ score

The prorated 7-day average DSQ score is calculated over a 7-day period using the formula as below:

$$\text{The prorated 7-day average DSQ score} = \frac{(\text{sum of points from questions 2 and 3 from daily DSQ diary}) * 7}{\text{number of diary days reported with non-missing data}}$$

The un-prorated 7-day average DSQ score is calculated over a 7-day period using the formula as below:

$$\text{The un-prorated 7-day average DSQ score} = \frac{(\text{sum of points from questions 2 and 3 from daily DSQ diary})}{\text{number of diary days reported with non-missing data}}$$

If there are less than 4 diary entries for a 7-day period, both the prorated and un-prorated 7-day average DSQ scores are considered to be missing for that period.

The un-prorated 14-day average DSQ score is calculated over a 14-day period using the formula as below:

$$\text{The un-prorated 14-day average DSQ score} = \frac{(\text{sum of points from questions 2 and 3 from daily DSQ diary})}{\text{number of diary days reported with non-missing data}}$$

If there are less than 8 diary entries for a 14-day period, the un-prorated 14-day average DSQ score is considered to be missing for that period.

The prorated DSQ scores are basically identical with the un-prorated DSQ scores with multiplier (7 or 14).

## **4.5. Safety Variables**

### **4.5.1. Adverse Events and Serious Adverse Events**

Adverse events and serious adverse events will be collected from the time of informed consent signature and then at each visit until the end of the study. All adverse events are to be coded using the Medical Dictionary for Regulatory Activities (MedDRA).

The definition of Adverse events and serious adverse events are referred to protocol section 9.3.1 and section 9.3.2. The pre-treatment AE and treatment-emergent AE (TEAE) is defined as following:

- Pre-treatment signs and symptoms (Pre-treatment AEs) are AEs that developed or worsened in severity during the pre-treatment period.
- Treatment-emergent AEs (TEAEs) are AEs that developed or worsened in severity compared to the baseline during the treatment-emergent period. As the worsening pre-existing AEs and new AEs that occur during the treatment and follow-up period will be collected on the AE case report form, all AEs with an onset date during the treatment and follow-up periods are considered as TEAEs.

The following AESIs will be analyzed:

- Anaphylactic reactions
- Systemic hypersensitivity reactions
- Helminthic infections
- Any severe type of conjunctivitis or blepharitis
- Keratitis
- Clinically symptomatic eosinophilia (or eosinophilia associated with clinical symptoms)
- Severe injection site reactions
- Herpes simplex infection
- Arthralgia

For detailed definition of these AESIs, please see Section 11.4.

#### 4.5.2. Laboratory Safety Variables

Hematology, chemistry, urinalysis, and pregnancy testing samples will be analyzed by a central laboratory. Samples will be collected predose at the initial screening visit (visit 1), baseline visit (visit 3), week 12, week 24, week 36, week 52 (EOS) or ET visits. Tests will include:

##### Blood Chemistry

Sodium	Total protein, serum	Total and indirect bilirubin
Potassium	Creatinine	Total cholesterol
Chloride	Blood urea nitrogen (BUN)	Low-density lipoprotein (LDL)
Carbon dioxide	AST	High-density lipoprotein (HDL)
Calcium	ALT	Triglycerides
Glucose	Alkaline phosphatase	Uric acid
Albumin	Lactate dehydrogenase (LDH)	Creatine phosphokinase (CPK) 

 CPK isoenzymes will be measured when CPK >5 × ULN

##### Hematology

Hemoglobin	Differential:
Hematocrit	Neutrophils
Red blood cells (RBCs)	Lymphocytes
White blood cells (WBCs)	Monocytes
Red cell indices	Basophils
Platelet count	Eosinophils

### **Urinalysis**

Microscopic analysis will only be done in the event of abnormal dipstick results.

Color	Glucose	RBC
Clarity	Blood	Hyaline and other casts
pH	Bilirubin	Bacteria
Specific gravity	Leukocyte esterase	Epithelial cells
Ketones	Nitrite	Crystals
Protein	WBC	Yeast

#### **4.5.3. Vital Signs**

Vital signs, including heart rate, blood pressure, respiration rate, and body temperature will be collected predose and 30 minutes post-dose at the initial screening visit (visit 1), every scheduled visit and the unscheduled visit before rescue treatment. Heart rate and blood pressure will be measured with the patient in a sitting position, after the patient has rested comfortably for at least 5 minutes. Weight is measured at the initial screening visit (visit 1), every scheduled visit (except week 1, week 40, week 44, and week 48 visits). Height is measured at the initial screening visit (visit 1), week 24, and week 52 (EOS) or ET visits.

#### **4.5.4. 12-Lead Electrocardiography (ECG)**

Standard 12-Lead ECG parameters include: Ventricular HR, PR interval, QRS interval, corrected QT interval (QTc Fridericia [QTcF] =  $QT/\sqrt[3]{RR}$  and QTc Bazett [QTcB] =  $QT/\sqrt{RR}$ ). Electrocardiogram results will be interpreted by a central reading center and categorized to: normal, abnormal not clinically significant or abnormal clinically significant.

ECG will be performed predose at the initial screening visit (visit 1), week 24, and week 52 (EOS) or ET visits. ECG will be performed before blood is drawn during visits requiring blood draws.

#### **4.5.5. Physical Examination Variables**

The physical examination variable values are dichotomized to normal and abnormal.

A thorough and complete physical examination will be performed at the initial screening visit (visit 1), week 24, and week 52 (EOS) or ET visits.

#### **4.6. Pharmacokinetic Variables**

Serum samples for measuring functional dupilumab concentrations will be collected at time points according to Section 11.2. PK variables consist of functional dupilumab concentration and time (both actual and nominal).

#### **4.7. Immunogenicity Variables**

The immunogenicity variables are ADA response status, titer, NAb response status, and time-point/visit.

ADA response are specifically defined as follows:

- ADA Negative, defined as an ADA negative response in the ADA assay at all time points collected, regardless of any missing samples.
- Pre-existing immunoreactivity, defined as either an ADA positive response in the dupilumab ADA assay at baseline with all post first dose ADA results negative, OR a positive response at baseline with all post first dose ADA responses less than 4-fold over baseline titer levels.
- Treatment-emergent response, defined as a positive response in the dupilumab ADA assay post first dose when baseline results are negative or missing. The treatment-emergent responses will be further characterized as Persistent, Indeterminate or Transient.
  - Persistent Response: Treatment-emergent ADA positive response with two or more consecutive ADA positive sampling time points, separated by greater than 12-week period (based on nominal sampling time), with no ADA negative samples in between, regardless of any missing samples.
  - Indeterminate Response: Treatment-emergent ADA positive response with only the last collected sample positive in the ADA assay.
  - Transient Response: Treatment-emergent ADA positive response that is not considered persistent or indeterminate, regardless of any missing samples.
- Treatment-boosted response, defined as a positive response in the dupilumab ADA assay post first dose that is greater than or equal to 4-fold over baseline titer levels, when baseline results are positive

Serum samples for ADA will be collected at the clinic visits specified in Section 11.2.

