## 5. STATISTICAL METHODS

For continuous variables, descriptive statistics will include the following: the number of patients reflected in the calculation (n), mean, median, Q1, Q3, standard deviation, minimum, and maximum.

For categorical or ordinal data, frequencies and percentages will be displayed for each category. Missing values at baseline will not be imputed unless otherwise specified.

All data will be summarized by the following treatment groups in each part:

1. Part B
  - Dupilumab 300mg Q2W
  - Dupilumab 300mg QW
  - Combined Dupilumab Group (For safety analysis only)
  - Placebo
2. Part C (Treatment in Part B/Treatment in Part C)
  - Dupilumab 300mg Q2W/Dupilumab 300mg Q2W
  - Dupilumab 300mg QW/Dupilumab 300mg QW
  - Combined Dupilumab Group (For safety analysis only)
  - Placebo/ Dupilumab 300mg Q2W
  - Placebo/ Dupilumab 300mg QW
  - Placebo/Dupilumab (For safety analysis only)
  - Total (For safety analysis only)

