## **5.9. Analysis of Immunogenicity Data**

### **5.9.1. Analysis of ADA**

The immunogenicity variables mentioned in Section 4.7 will be summarized using descriptive statistics. Immunogenicity will be characterized by ADA responses as defined in Section 4.7 and titers observed in patients in the ADA analysis set.

The following listings will be provided:

- Number (n) and percent (%) of ADA-negative patients that are negative in the ADA assay at all time points by treatment groups

- Number (n) and percent (%) of patients with Pre-existing immunoreactivity by treatment groups
- Number (n) and percent (%) of treatment-emergent ADA positive patients by treatment groups and ADA titer categories
  - Number (n) and percent (%) of persistent treatment-emergent ADA positive patients
  - Number (n) and percent (%) of indeterminate treatment-emergent ADA positive patients
  - Number (n) and percent (%) of transient treatment-emergent ADA positive patients
- Number (n) and percent (%) of treatment-boosted ADA positive patients by treatment groups and ADA titer categories

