**5.10. Association of Immunogenicity with Exposure, Safety and Efficacy**

The analyses in this section will only be performed if incidence of treatment emergent ADA positive is sufficient to make meaningful conclusions (i.e. more than 5% in any treatment group).

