**Table 2: Analysis Visit Window for Safety and Biomarkers in Part B**

Visit from SOE	Target Study Day in Part B a	Analysis Window based on Study Day in Part B					
		Vital signs	Weight	Physical examination, ECG, Height	Laboratory, PK, ADA	Eotaxin-3, Total IgE, Allergen-specific IgE, IgG4	TARC
Baseline	1	≤1	≤1	≤1	≤1	≤1	≤1
Week 1	8	[2, 11]					
Week 2	15	[12, 22]	[2, 22]				
Week 4	29	[23, 43]	[23, 43]			[2, 57]	[2, 89]
Week 8	57	[44, 71]	[44, 71]				
Week 12	85	[72, 99]	[72, 99]		[2, 113]	[58, 127]	
Week 16	113	[100, 127]	[100, 127]				
Week 20	141	[128, 155]	[128, 155]		[114, 155]		
Week 24 (Part B end of treatment)	169	[156, 190] Error! Reference source not found.	[156, 190] Error! Reference source not found.	[2, 190] Error! Reference source not found.	[156, 190] Error! Reference source not found.	[128, 190] Error! Reference source not found.	[90, 190] Error! Reference source not found.
Week 28 c (Extended period of Part B)	197	[191, 204]					
Week 30 c (Extended period of Part B)	211	[205, 218]					
Week 32 c (Extended period of Part B)	225	[219, 232]					
Week 34 c (Extended period of Part B)	239	[233, 246]					
Week 36 c (Extended period of Part B)	253	≥247					

a **Error! Reference source not found.** Study days are calculated from the day of 1st injection of Part B. Study day = (date of assessment – 1st injection date +1) when date of assessment ≥ 1st injection date; otherwise study day = (date of assessment – 1st injection date). If patient never received any dose of study drug, randomization date will be used in place of 1st injection date.

b **Error! Reference source not found.** If unscheduled or ET visit occurs in this window and it is after the first dose of Part C, it will be considered for Week 26.

c Those are dummy analysis visits windows for patients with extended dosing in Part B. ET or unscheduled visit occurred after week 24 visit and before first dose of part C will be mapped per Table 5.

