## **8. TIMING OF STATISTICAL ANALYSIS**

Primary analysis and final analysis are planned for Part B patients. The primary analysis will be performed when the last Part B patient has completed their end of Part B visit including patients who have terminated early in Part B. The assessments of primary, secondary, and exploratory efficacy endpoints through the end of Part B during the primary analysis will be the final (and only) analyses of these endpoints. Hence, there will be no need for alpha adjustment due to this primary analysis. Available Part B patients' Part C data will also be analyzed and evaluated, including assessment of secondary endpoints at week 52 for patients for whom this is evaluable at time last patient completes end of Part B. The final analysis for Part B patients will occur when all patients who entered the 12-week follow-up period immediately from Part B or Part C completed the follow-up period. The Part B CSR will be written separately from Part B patients' Part C CSR.

To maintain study integrity with respect to the post Part B visits and analyses, a dissemination plan will be written. This plan will clearly identify the team (including the statistician) that will perform the Part B analysis and all related activities, restrict other clinical team members and other Sponsor personnel from access to individual patient treatment allocation and site level analysis results, and ensure that the dedicated team will not participate in the data review or data decisions for the following post treatment analyses. However, the dedicated team can participate in the analysis following the final database lock.

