**Table 8: Follow-up Period, Early Termination Visit, and Unscheduled Visit**

Study Procedure	12-Week Follow-Up EOS Visit	Early Termination during 12-Week Follow-Up1	Early Termination during Parts A, B, or C1	Unscheduled Visit before Rescue Treatment	Unscheduled Visit for Other Reasons
Week (W)	12 weeks after EOT visit				
Day (D)	84 days after EOT visit				
Visit Window (Days [d])	±7 d				
Concomitant medications/procedures 	X	X	X	X	X
Efficacy:					
DSQ eDiary 	←completed daily by patient→		X	X	
PGIC 			X	X	
PGIS 			X	X	
EoE Impact Questionnaire 			X	X	
EoE Symptom Questionnaire 			X	X	
TNSS 			X	X	
RQLQ(S)+12 			X	X	
ACQ-5 			X	X	
POEM 			X	X	
EoE-EREFS 			X 7, 7a	X 	
Endoscopy with biopsies (histology, IHC, RNA) 			X 7, 7a	X 	
Safety:					
Vital signs	X	X	X	X	
Height 			X		
Weight	X	X	X		
Physical examination			X		
ECG			X		
Adverse events	X	X	X	X	X
Laboratory Testing:					
Hematology, Chemistry	X	X	X		
Pregnancy test	Urine	Urine	Urine		
Urinalysis	X	X	X		

PK and ADA:					
PK Sample	X	X	X	X	
ADA sample	X	X	X	X	X
Biomarkers:					
Future Biomarker Serum/Plasma (optional)			X		

ADA = anti-drug antibody; DSQ = Dysphagia Symptom Questionnaire; ECG = electrocardiogram; EoE-EREFS = Eosinophilic Esophagitis-Endoscopic Reference Score; EOS = end of study (visit); EOT = end of treatment period; POEM = Patient-Oriented Eczema Measure; PRO = patient-reported outcome; PGA = physician global assessment; PGIC = Patient Global Impression of Change of Dysphagia; PGIS = Patient Global Impression of Severity of Dysphagia; PK = pharmacokinetic; RQLQ(S)+12 = Rhinoconjunctivitis Quality of Life Questionnaire for patients aged 12+ years; TNSS = Total Nasal Symptom Score

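### Part B patients who are ADA-positive at both scheduled post-baseline samples are classed as transient, because the samples are exactly 12 weeks apart and persistence requires more than 12

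*SAP*

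**What the plan says.** SAP 4.7 divides treatment-emergent ADA responses (baseline negative or missing) into three classes.

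- **Persistent** needs "two or more consecutive ADA positive sampling time points, separated by greater than 12-week period (based on nominal sampling time"), with no negative sample in between.
- **Indeterminate** applies when the last collected sample is the only positive one.
- **Transient** is the remainder: "Treatment-emergent ADA positive response that is not considered persistent or indeterminate".

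SAP Table 6 and protocol Table 1 schedule ADA samples in the double-blind period at baseline, week 12 and week 24 only. SAP Table 8 adds a sample at the follow-up visit, "84 days after EOT visit".

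SAP 5.9.1 plans a row for "Number (n) and percent (%) of persistent treatment-emergent ADA positive patients" alongside indeterminate and transient rows. SAP 5.10.2 lists persistent response as a category for exploring associations with safety and efficacy.

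On scope, SAP 5 states: "All data will be summarized by the following treatment groups in each part". SAP 8 adds: "The Part B CSR will be written separately". The Part B heading in SAP 6.4 bars data from after the first Part C injection from the Part B analysis.

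**The concern.** The cut-off coincides with the sampling interval, and the inequality is strict. A patient positive at every post-baseline sample in Part B gets the same label as one who was positive at week 12 and had cleared by week 24. Because the rule runs on nominal time, a slightly late visit that keeps its week 24 label does not escape it.

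Immunogenicity is a secondary objective. A zero in the Part B persistent row would read as evidence that no patient had sustained ADA, when the definition alone produces that zero for on-schedule samples. The transient row would mix sustained with cleared responses, and so would any comparison of safety or efficacy by these classes.

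**Working it through.** **Inputs.** Nominal days from SAP Tables 6 and 7: week 12 = day 85, week 24 = day 169, week 32 = day 225, week 52 = day 365. Each agrees with day = 7 × week + 1. The follow-up sample is due 84 days after the end-of-treatment visit, i.e. nominal week 36 for patients who skip Part C (169 + 84 = 253 = 7 × 36 + 1) and nominal week 64 after Part C (365 + 84 = 449 = 7 × 64 + 1).

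**Gaps between adjacent scheduled samples.**

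- Week 12 to week 24: 169 − 85 = 84 days = 12 weeks
- Week 24 to week 32: 225 − 169 = 56 days = 8 weeks
- Week 32 to week 52: 365 − 225 = 140 days = 20 weeks
- Week 24 to follow-up: 84 days = 12 weeks
- Week 52 to follow-up: 84 days = 12 weeks

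Three of the five gaps equal the cut-off exactly.

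**Part B scheduled samples (week 12, week 24), baseline negative.**

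- (+,−): transient
- (−,+): indeterminate
- (+,+): 12 is not greater than 12, so not persistent; two positives, so not indeterminate; hence transient

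These are all 3 patterns with a positive. If one sample may be missing there are 5, since (+, missing) and (missing, +) are added; neither can be persistent with a single positive. Replacing > 12 by ≥ 12 changes only (+,+), which becomes persistent.

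**Other sample sets.** SAP 4.7 does not say whether the separation is measured from the first to the last positive of a run or between neighbouring positives. The table uses first to last unless marked.

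| Samples (nominal weeks) | Patterns with a positive | Persistent, > 12 | Persistent, ≥ 12 | Patterns that change |
|---|---|---|---|---|
| Part B: 12, 24 | 3 | 0 | 1 | (+,+) |
| Part B and follow-up, no Part C: 12, 24, 36 | 7 | 1 | 3 | (+,+,−), (−,+,+) |
| Same, neighbouring positives | 7 | 0 | 3 | (+,+,+), (+,+,−), (−,+,+) |
| Part C: 32, 52 | 3 | 1 | 1 | none |
| Part C and follow-up: 32, 52, 64 | 7 | 2 | 3 | (−,+,+) |
| Parts B and C pooled: 12, 24, 32, 52 | 15 | 5 | 7 | (+,+,−,−), (+,+,−,+) |

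**Extended dosing.** SAP Table 2 has windows at weeks 28 to 36, of which it says "Those are dummy analysis visits windows for patients with extended dosing in Part B". These lie 28 − 12 = 16 to 36 − 12 = 24 weeks after week 12, so a patient sampled there can be persistent.

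**Trigger for the association analysis.** SAP 5.10 requires treatment-emergent incidence of "more than 5% in any treatment group". With about 70 patients per group, 5% × 70 = 3.5, so at least 4 patients.

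**The case against.** The strongest objection is scope. SAP 4.7 is worded at patient level and does not restrict the classification to one study part. SAP 3.4 uses part-specific wording, but only for membership of the analysis set. SAP 8 also says that available Part C data from Part B patients will be analyzed at the primary analysis. If Part C samples counted, a patient positive at weeks 12, 24 and 32 would span 20 weeks and be persistent. For the Part B analysis this does not succeed: SAP 5 summarizes by part, and the SAP 6.4 heading excludes data from after the first Part C injection. It does stand that SAP 4.7 should name the samples that count.

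Follow-up samples rescue the class only in part. Among patients who skip Part C, only those positive at weeks 12, 24 and 36 become persistent, and only on the first-to-last reading. A patient first positive at week 24 and still positive at follow-up is again at exactly 12 weeks. Extended-dosing samples, and unscheduled samples if classified at their own time, are genuine exceptions, but they do not help on-schedule patients.

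The strict cut-off may also be deliberate, and nothing in the documents shows it to be a slip. Part A has a separate SAP, not available here, which may use the same definition. In that case the strict rule can stay, but the Part B table then needs a note that its persistent row cannot be filled from scheduled samples.

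Finally, the objective covers up to 52 weeks, and persistence can be reached in Part C, where weeks 32 and 52 are 20 weeks apart. That limits the importance of the point; it does not correct the Part B rows.

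**Conclusion.** The concern holds and is minor. With on-schedule Part B samples and part-specific reporting, no result pattern can be persistent, and patients positive throughout are counted as transient. The conclusion rests on three readings: the strict inequality is applied literally on nominal time, the Part B classification uses Part B treatment-period samples, and the visits follow the schedule.

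The effect is confined to the descriptive split in SAP 5.9.1 and to the association work in SAP 5.10, which is both conditional and optional. Treatment-emergent incidence, titer categories and neutralizing-antibody results do not change, and no hypothesis test uses these classes. How many patients would be reclassified is unknown.

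**What to change.** In SAP 4.7, define persistence by the first and last positive samples of the run being at least 12 weeks apart on nominal time. This settles both the inequality and the meaning of separation.

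Add one sentence saying which samples enter the Part B classification: for example, those up to the end of the Part B treatment period, with follow-up samples summarized separately, or the reverse if that is intended. Under the first choice, a patient who skips Part C and is positive only at week 24 and at follow-up is indeterminate in Part B; under the second, persistent.

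If strictly more than 12 weeks is intended, keep the rule and state under the Part B table that persistence cannot be assessed from the scheduled samples. Check the Part A SAP so that the two parts use the same definition, or say why they differ.

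The cost is one phrase and one sentence in the SAP, plus the matching condition in the program. No new samples or data are needed.
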